## 5 Data Analysis

Describe the data analysis plan, including any statistical procedures or power analysis.

The data will be randomly assigned with serial ID numbers. All tests will be assumed two-sided and an alpha level of .05 will be used. SAS 9.4 will be used for data processing and all statistical analyses. Missing data will be handled by multiple imputations of dependent values. 101–103 Analyses just of complete data will be conducted and comparisons of groups with and without missing data will be made. In addition, sensitivity analyses of complete data will be conducted and compared imputed data analysis. An **intent-to-treat** analysis will be employed. For **Hypotheses 1 to 3**, differences in continuous outcome measures over time will be examined using **linear mixed-effects modeling.** In particular, we will fit mixed effects models to each continuous outcome measure. We will use random intercepts as well as explore random slopes to represent subject level variability. Fixed-effects corresponding to group, time and group x time interaction will be included in the model. A significant group x time interaction will indicate substantial differences in the groups over time. Restricted maximum likelihood method will be used for estimation, and the most appropriate covariance structure will be examined.

Since Data and Safety Monitoring Boards (DSMBs) are required only for phase III clinical trials (NOT-OD-00-038.html), we do not include a DSMB for this intervention study. For the proposed intervention study, we have

the following data safety monitoring plan (DSMP). First, to manage and protect the data collected, only summary data will be openly accessible to funding agency or will appear in publications. Research participants will be informed that they are free to decline to answer any questions they do not wish to answer or to stop participating in the project at any time. When a participant withdraws from participation, the data that they have provided will be immediately removed. Also, the data will have no identifying information to link a subject to the data.

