
A Walk Through Dementia - walking home (3 minutes 20 seconds) https://www.youtube.com/watch?v=R-Rcbj qR4g&ab channel=AlzheimersResearchUK).

A Walk Through Dementia - at the supermarket (4 minutes 52 seconds) https://www.youtube.com/watch?v=TaeNgo8bR2k&ab\_channel=AlzheimersResearchUK

A Walk Through Dementia - at home (2 minutes 34 seconds) https://www.youtube.com/watch?v=2EO7Dh3fM7Y&ab channel=AlzheimersResearchUK

TACAD also has self-adaptation functionality based on Genetic Algorithm such that the program can deliver the most relevant and effective educational modules and online resources to each participant by using a machine learning method. Cultural tailoring was theoretically guided by the criteria for rigor in cross-cultural research. Based on the criteria, TACAD incorporated specific components to: (a) respect cultural uniqueness; (b) understand cultural contexts; (c) use cultural examples; (d) have flexibility; (e) adopt multiple languages; (f) have culturally matched bilingual research team members; and (f) engage community consultants and research participants. Presentation styles were tailored to Asian culture. Through the process, both surface and in-depth cultural tailoring was done. TACAD used a free-form matrix information architecture and included menus based on the four components. *Graphic User Interface controls*,  the *Ruby on Rails (ROR)* framework, and the Xen hypervisor were used. Due to the use of ROR, different language versions could be easily added to the program, and cultural

tailoring methods used in this program could been easily adopted to different sub-ethnic groups. All the usages of different components will be automatically recorded in the server, which will allow the evaluation of different components. For instance, the usages of individual educational modules will be recorded on the server, so the association of the usages of specific modules to outcome variables could be easily determined later. To assess contamination, we will gauge crosstalk by open-ended questions about it at T1&2. We will estimate its effects statistically by testing if intervention effects are weaker among those who crosstalk.

[figure not shown]
Alzheimer's Association (AA) Website. The AA website has information in various areas related to AD and caregiving

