For instance, the webpage on caregiving includes information on caregiving, care option, financial/legal planning, caregiver health, daily care, stages and behaviors, and safety. The content will be available in the three languages at the project website. The usages of the AA website and additional information searches (the participants will use them only through the project website) will be automatically recorded through the project server and later used for data analyses. Both groups will be asked to maintain their usual care. The interventionists will weekly remind the control group to use the AA website.

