## **15** Sample size rationale

Describe your sample size rational below.

To test Hypotheses 1 to 3 (Aim 2), with 80% power and a type I error rate equal to 0.00625 to account for 9 outcome measures modeled within two hypotheses, group sample sizes of 105 each will have enough power to detect a difference of 0.5 between group means overall in the follow-up period. However, considering the proposed study period, limited budget, and the inherent explorative nature of the study, we will include only 60 (30 per group) women; 30 will be adequate for a pilot intervention study.

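### The planned crosstalk test splits women on a self-reported, post-randomisation variable; it cannot reliably detect or exclude contamination and can point the wrong way

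*Combined protocol and SAP*

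**What the plan says.** The contamination plan is two sentences in Procedure Description, Phase 2 (Aim 2), at the end of the TACAD description. The first covers measurement: "To assess contamination, we will gauge crosstalk by open-ended questions about it at T1&2". The second covers analysis: "We will estimate its effects statistically by testing if intervention effects are weaker among those who crosstalk".

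Section 5 (Data Analysis) specifies an intent-to-treat linear mixed model with group, time and their interaction, and says "All tests will be assumed two-sided and an alpha level of .05 will be used". It does not mention crosstalk. Nowhere do the documents define crosstalk separately for each arm, say how the open-ended answers will be coded, or say what conclusion follows from the test.

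The same Phase 2 text gives TACAD to the intervention group only, and makes peer posting on a social media site one of its components. The recruitment section allows snowball sampling and word of mouth, so acquaintances may end up in different arms.

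**The concern.** Contamination acts through control women who receive TACAD content. The planned test looks instead at whether the arm difference is smaller among crosstalkers of both arms than among the rest. That raises two problems.

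- The split is made on something women do and report after randomisation. Within crosstalkers, the TACAD and control women are two self-selected groups, and randomisation no longer makes them comparable.
- The label covers different behaviour by arm. For a control woman, crosstalk is possible exposure. For a TACAD woman, it is passing content on, and it may mark a more engaged user who would do better anyway.

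At stake is how the pilot is read. If the main comparison shows little difference, the team will want to know whether controls were exposed. A contrast driven by who chooses to talk could give false reassurance or a false alarm.

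**Working it through.** **Inputs.** From Section 15: 30 women per group and a target difference of 0.5. From Section 5: two-sided 0.05. Assumed, because the documents give no figures: SD = 1; share of women who crosstalk, p, from 10% to 50%, equal in both arms; share of the effect reaching a crosstalking control, c = 0.5 or 1; one follow-up measure.

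**The plan's own figure.** Section 15 says "group sample sizes of 105 each will have enough power" to "detect a difference of 0.5 between group means overall in the follow-up period", "with 80% power and a type I error rate equal to 0.00625 to account for 9 outcome measures". With SD = 1, a two-sided noncentral-t calculation gives 105 per group (power 80.4%). So 0.5 can be read as 0.5 SD. The documents give no figure for the crosstalk test.

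**Expected value of the contrast.** Let dT and dC be how much better crosstalkers would do than non-crosstalkers in the TACAD and control arms, apart from any contamination. Then

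interaction = (effect in crosstalkers) − (effect in others) = −0.5c + (dT − dC).

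- If dT = dC, the interaction is −0.25 for c = 0.5 and −0.50 for c = 1: right sign and size.
- The sign reverses only when dT − dC exceeds 0.5c, that is 0.25 SD for half contamination and 0.50 SD for full.
- For example, dT − dC = 0.3 gives −0.25 + 0.30 = +0.05 (wrong sign) under half contamination, but −0.50 + 0.30 = −0.20 (right sign) under full.

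**Power when there is no differential selection.** SE = sqrt(2 × [1/(30p) + 1/(30(1−p))]). At p = 20% there are 6 crosstalkers and 24 others per arm, so SE = sqrt(2/6 + 2/24) = 0.645 SD. Noncentral t, 56 df, two-sided 0.05:

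| p | SE | power, c = 0.5 | power, c = 1 |
|---|---|---|---|
| 10% | 0.861 | 5.9% | 8.8% |
| 20% | 0.645 | 6.7% | 11.9% |
| 30% | 0.563 | 7.2% | 14.1% |
| 50% | 0.516 | 7.6% | 15.9% |

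At p = 20% the point estimate has the wrong sign in about 35% of trials for half contamination (normal probability below −0.25/0.645) and about 22% for full. By normal approximation, 80% power against full contamination would need about 393 women per arm at p = 20%, 300 at 30% and 252 at 50%.

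**Simulation with selection.** True effect 0.5, 30% crosstalk per arm, a latent tendency to improve correlated 0.5 with outcome, and crosstalk log-odds of ±1 per SD of that tendency (all assumed except 0.5):

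| Situation | Effect in crosstalkers | Effect in others |
|---|---|---|
| Half contamination, no selection | 0.25 | 0.50 |
| Half contamination, same selection in both arms | 0.25 | 0.50 |
| No contamination, controls likely to improve crosstalk more | 0.21 | 0.63 |
| Half contamination, engaged TACAD women crosstalk more | 0.55 | 0.37 |
| Full contamination, engaged TACAD women crosstalk more | 0.30 | 0.38 |
| Full contamination, engaged TACAD women and struggling controls crosstalk more | 0.59 | 0.25 |

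The third row is a false alarm. The fourth and sixth show real contamination as a stronger effect; in the sixth the intent-to-treat effect is meanwhile diluted to 0.5 × (1 − 0.3) = 0.35. The first two rows show that the contrast is not always wrong.

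**The case against.** The best defence is that this is a supplementary check in a pilot that Section 15 openly calls explorative. Low power is not peculiar to it: at 30 per arm the main comparison itself has only about 48% power for 0.5 SD at two-sided 0.05. The check changes no primary estimate. The wrong sign depends on selection that I assumed; if women crosstalk for similar reasons in both arms, the bias cancels. The plan also states no decision rule, so nobody has committed to reading a null as proof of no contamination.

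All of this stands, and it limits the point. It does not rescue the test as an estimate of contamination. The plan says that it will estimate the effect of crosstalk in this way, offers no argument that selection is alike in the two arms, and gives reasons to expect otherwise, since only one arm has TACAD and a peer forum.

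Two stronger readings should be resisted. A reader might infer that the test can never detect contamination. The formula and the first two simulation rows contradict that: the test is then underpowered, not blind. A reader might also infer that the plan has no other protection against contamination. It has design safeguards: account and password access, postings visible only on the project website, and exclusion of earlier users of the Alzheimer's Association website. The crosstalk test is the only stated analysis of crosstalk, which is a narrower statement.

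**Conclusion.** The concern holds as a problem of validity and interpretation. Followed as written, the plan labels a non-randomised contrast as the effect of contamination. Under the stated assumptions (30 per arm, SD = 1, 10% to 50% crosstalk) it would find half contamination in about 6% to 8% of trials and full contamination in 9% to 16%. Its sign reverses under half contamination only if differential selection exceeds 0.25 SD. No figure in the documents says whether selection would be that large, so reversal is a risk and not a prediction.

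A reader might infer that the primary result is biased by this test. It is not: the intent-to-treat estimate does not depend on it. Contamination itself would dilute that estimate, and this check is a poor guide to whether it did. The change is worth making before analysis, but it is not critical to the trial.

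**What to change.** 1. Remove the test as the estimate of contamination. Alternatively, keep it labelled exploratory and non-causal, with its assumption of equal selection in both arms stated and a sentence saying that a non-significant result is not evidence of no contamination.
2. Code the T1 and T2 crosstalk answers by arm and direction: control women who received TACAD content, and TACAD women who passed it on. Report the number and share of control women exposed.
3. Keep the intent-to-treat estimate as the result.
4. Optionally, add the intent-to-treat difference divided by the between-arm difference in the share exposed, with its confidence interval, labelled an upper bracket. It counts partial second-hand exposure as full exposure. At 20% crosstalk and half contamination, the intent-to-treat difference is 0.5 × (1 − 0.2 × 0.5) = 0.45 and the ratio is 0.45/0.80 = 0.56, against a true 0.50. It also relies on self-report, because server logs do not record conversations between women. It cannot separate an ineffective program from contaminated controls, since a difference near zero stays near zero after division.

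The cost is a few lines of SAP text, some coding of answers already planned, and at most one extra calculation, whose interval will be wide with 60 women.

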
## 4 Design and Methodology

Provide a brief description of the study design or data collection methodologies. Details regarding protocol specific research procedures will be discussed in a later section.

The study includes two phases: (a) a usability test and an expert review (Phase 1) and (b) a pilot randomized clinical trial (Phase 2). Phase 1 has been completed at Emory, and only Phase 2 will be conducted at Univ. of Texas at Austin (UT Austin). For Phase 2, the data will be collected at three points: (a) pre-test; (b) post 1 month; and (c) post 3 months. The collected data will be analyzed after the data collection of all the participants is completed.

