Instruments. The instruments to measure caregivers' health outcomes (primary outcomes; Hypothesis 1) include: (a) Multidimensional Caregiver Strain Index, Perceived Stress Scale, Acculturation Stress Scale (ASS), 148 and Social Readjustment Rating Scale (SRRS)  (to measure stress); (b) the Women's Symptom Index (to measure physical and psychological symptoms); and (c) EQ-5D-5L(to measure the quality of life). The instruments to measure care recipients' health outcomes (primary outcomes; Hypothesis 1) will include: (a) Informant Questionnaire on Cognitive Decline in the Elderly (IQCODE)(to measure the cognitive status of care recipients); (b) Lawton ADL/IADL Scale (to measure PLAD's activities of daily life); (c) Revised Memory and Behavior Problem Checklist (to measure behavioral and psychological symptoms of care recipients); (d) Neuropsychological Inventory Questionnaire (to measure care recipients' mood status); and (e) Quality of Life Scale in Alzheimer's Disease (to measure care recipients' quality of life). The instruments to measure caregiving experience (secondary outcomes; Hypothesis 2) will include: (a) Caregiver Activity Survey (to measure caregiving activity); (b) Ways of Coping Scale (to measure coping); (b) Pearlin Mastery, Loss, and Competence Scale (to measure caregivers' mastery of caregiving competence); and (c) Caregiver Assessment of Behavioral Skill Scale (to measure caregiving skills). 163 The theory-based variables (attitudes, self-efficacy, perceived barriers, & social influences; Hypothesis 3) will be measured using the modified Questions on Attitudes, Subjective Norm, Perceived Behavioral Control, and Behavioral Intention (QASPB). 164 Covariates that will be considered in determining the effect of TACAD on outcome variables include caregivers' sociodemographic characteristics and caregiving history (e.g., socioeconomic status, PLAD information, length of caregiving, co-residence with recipient). The reliability and validity of all the instruments have been established among Asian Americans. Cronbach's alpha of the instruments ranged from .70 to .96 among Asian Americans. Because no existing instruments have culture-specific measures, we will add open ended questions to all the measures to explore culture specific aspects that are missing in the specific measures. The same questionnaire will be used at the three time points except the questions on sociodemographic characteristics and caregiving history (e.g., socioeconomic status, PLAD information, length of caregiving, co-residence with recipient). The questions on sociodemographic characteristics and caregiving history (e.g., socioeconomic status, PLAD information, length of caregiving, co-residence with recipient) will be asked only at the pre-test. This has been clarified on p. 10.

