#### d Inclusion Criteria

Participants will be included if, by self-report, they are Asian American women who identify as Chinese or Korean; are caregivers of PLAD; can read and write English, Mandarin Chinese or Korean; and have access to the Internet through computers or mobile devices. Participants must be providing assistance for the PLAD in the early-middle stage of illness (Clinical Dementia Rating of  $\geq$  1) for whom there is no plan for institutionalization in six months. Caregivers may or may not reside with their care recipient.

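### No planned item at 1 or 3 months records whether the care recipient is alive, where she or he lives, or whether the woman still provides care, and the imputation rule makes no exception for these events

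*Combined protocol and SAP*

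**What the plan says.** Section 4 (Design and Methodology) sets three data-collection points: "a) pre-test; (b) post 1 month; and (c) post 3 months". The Instruments text of Phase 2 (Aim 2) then states that "The same questionnaire will be used at the three time points except the questions on sociodemographic characteristics and caregiving history", and repeats the restriction: "PLAD information, length of caregiving, co-residence with recipient) will be asked only at the pre-test".

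The scales that are repeated include the caregiver strain index, the Caregiver Activity Survey ("to measure caregiving activity") and five instruments on the recipient, introduced by "The instruments to measure care recipients' health outcomes (primary outcomes; Hypothesis 1) will include". The same text adds free-text questions: "we will add open ended questions to all the measures to explore culture specific aspects that are missing in the specific measures".

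The inclusion criteria require a recipient "for whom there is no plan for institutionalization in six months". Section 5 (Data Analysis) specifies an intent-to-treat analysis and says "Missing data will be handled by multiple imputations of dependent values". It also plans complete-data analyses, to be compared with the imputed results, and a comparison of women with and without missing data.

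**The concern.** The strain index, the Caregiver Activity Survey and the five recipient scales all presuppose a living recipient and a woman who is still caring. Over three months a recipient may die or be placed without prior plan, or care may pass to another relative. The entry criterion asks only about plans at enrolment and covers none of these.

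Two errors can follow.

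- **Recipient scales.** After a death they would probably be left blank. Section 5 as written would then impute function, behaviour, mood and quality of life for a person who is no longer alive.
- **Care-specific scales.** If a woman stops caring, her strain or activity score may fall for that reason alone. Under Hypotheses 1 and 2 the fall would be read as improvement, and no planned variable would mark it as something else.

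Status that is not asked for at the time cannot be reliably rebuilt later.

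**Working it through.** **1. Is the status recorded or handled anywhere else?**

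- *Instruments text, Phase 2 (Aim 2):* information on the recipient and on co-residence is confined to the pre-test. The added free-text questions are aimed at cultural content, not at status.
- *Inclusion criteria:* these look at plans on entry only.
- *Sections 33 and 34 (data safety monitoring):* usage, progress and adherence are reviewed. Recipient death, placement and end of caring are not listed.
- *Section 35 (Early Withdrawal):* these events are not listed.
- *Section 5:* imputation and intent-to-treat are stated, with no rule for these events.
- *Contact with staff:* weekly chat coaching is recommended for the intervention group only; the control group gets weekly reminders to use the Alzheimer's Association website. Any informal disclosure is unstructured and could differ by arm.

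No status item and no analysis rule is described.

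**2. The plan's own design figure.** Section 15 gives 105 per group for 80% power at a type I error of 0.00625 and a difference of 0.5. Taking the SD as 1 (an assumption; the section gives none) and a two-sided test:

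n = 2 × (2.734 + 0.842)² / 0.5² = 102.3, so 103 per group by the normal approximation; the noncentral t gives 105. The figure reproduces, and this point does not dispute it. It supports reading the 0.5 in SD units. The trial actually enrols 30 per group.

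**3. Size of the effect.** The event rate is not in the documents. If 2% to 10% of 60 women were affected (assumed), that would be 60 × 0.02 = 1.2 to 60 × 0.10 = 6 events. Let k be the excess number of events in one arm and s the score shift in SD (assumed 1 to 2):

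shift in the arm difference = k × s / 30

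| k | s = 1 | s = 2 |
|---|---|---|
| 1 | 0.033 | 0.067 |
| 2 | 0.067 | 0.133 |
| 3 | 0.100 | 0.200 |

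The standard error for one unadjusted comparison with SD 1 is √(2/30) = 0.258 SD. One excess event is therefore 0.033/0.258 = 0.13 to 0.067/0.258 = 0.26 of a standard error.

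**4. How likely is an uneven split?** With three events in all and no effect of treatment on them, the chance that all three fall in one arm is 2 × C(30,3) / C(60,3) = 8120 / 34220 = 0.237, ignoring stratification by sub-ethnic group. In the other 76% the split is 2 to 1, so k = 1 and the net shift is 0.033 to 0.067 SD.

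**The case against.** Asking covariates once, at baseline, is sound practice, so the quoted sentence is not itself the defect. The documents name the scales but do not reproduce their items, so one cannot rule out that the life-events scale or the Caregiver Activity Survey would hint at a bereavement or at no care given. Final materials are still to be uploaded by modification. Under intent-to-treat, a caregiver's own stress, symptoms and quality of life count whatever happens after randomization. Section 5 also plans complete-data analyses beside the imputed ones. The study is a pilot with early-to-middle-stage recipients and three months of follow-up, so events may be few.

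Much of this stands, and it limits the point. It does not remove it. An incidental hint in a stress scale is not a status variable, and the plan does not use it as one. A complete-data analysis cannot separate a blank caused by death from any other blank, or flag a completed strain scale from a woman who no longer cares.

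A reader might infer four stronger things that the documents do not support:

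- That such events would be wholly invisible or beyond any repair. Free-text answers, participant feedback, coaching chats and daily monitoring could surface some.
- That the entry criterion shows the investigators saw this threat. No reason for the criterion is given.
- That the estimate could be off by 20% to 40% of the 0.5 design difference. That needs three events, all in one arm, each shifting scores the same way by 1 to 2 SD. Grief could raise stress instead.
- That the comparison is biased on average. If treatment does not affect these events, the expected difference between arms from this source is about zero.

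**Conclusion.** The point holds in a limited form. The plan describes no status item at 1 or 3 months and no analysis rule for recipient death, placement or end of caring. Followed literally, it imputes primary recipient outcomes after a death, and it leaves lower strain or activity scores after caring ends indistinguishable from response in the planned data.

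The numerical effect is probably small: 0.03 to 0.07 SD per excess event, against a standard error of about 0.26 SD. It becomes material only if several events fall unevenly between arms. This rests on an assumed shift of 1 to 2 SD, 30 women analysed per arm and an SD of 1; the event rate is unknown. The case for acting is less the expected bias than that imputed scores after death have no meaning and that the missing information is cheap to collect now and hard to recover later. It is a worthwhile improvement, not a flaw that invalidates the trial.

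**What to change.** 1. **Instruments text, Phase 2 (Aim 2).** Keep the covariate block at baseline. Add short status items to the 1- and 3-month questionnaires: whether the recipient is alive (and the date of death if not), current living setting, whether the woman still provides care, and current co-residence. The plan already adds crosstalk questions at both follow-ups, so there is a precedent.
2. **Section 5.** State that recipient outcomes are not imputed after the recipient's death, and that care-specific items are not imputed once they no longer apply. Name the scales that count as care-specific.
3. **Analysis set.** Keep every woman in the intent-to-treat analysis of her own health outcomes.
4. **Reporting.** Give the number of these events by arm, and add one supportive analysis that uses data only up to the event.

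The cost is about one more minute per questionnaire, one IRB modification and one extra analysis. Sample size and randomization do not change.
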